## 1 PURPOSE

This Statistical Analysis Plan (SAP) describes the planned analysis and reporting for protocol Batten-1-01: An Open-label Safety, Pharmacokinetic, and Efficacy Study of Miglustat for the Treatment of CLN3 Disease in Patients 17 Years of Age and Older.

This SAP should be read in conjunction with the study protocol, case report form (CRF), and any other applicable study documents. This version of the SAP is based on the protocol Batten-1-01, v5.0 dated 06Feb2024 and CRF, v4.0 dated 12Feb2024. Changes to these documents may result in subsequent changes to the SAP. The final, sponsor-approved version of the SAP must occur prior to database lock.

### 1.1 Changes to the Planned Analyses

The following changes from the protocol were made in this SAP:

1. Adverse Event summaries are presented by system organ class (SOC), high level group term (HLGT) and preferred term (PT) as per Sponsor request, instead of presenting by SOC and PT. HLTG is added to provide more information.
2. According to the protocol, Medical Dictionary for Regulatory Activities (MedDRA; dictionary Version 21.1) and World Health Organization (WHO) Drug Dictionary Version SEP 2018 B3 GLOBAL will be used for coding of adverse events, medical history and medications. In practice, the most recent versions of MedDRA and WHODD available ahead of database lock will be used for coding.

## 2 INTRODUCTION

The Sponsor has identified a novel therapy that it believes holds particular promise for the treatment of juvenile Batten disease (CLN3). The Sponsor's product, Batten-1 is oral miglustat.

CLN3 disease is an ultra-rare, genetic, lysosomal storage disease that primarily affects the nervous system and is fatal. Children with CLN3 disease develop normally, even excelling in school until ages 4 to 7 years, when progressive vision loss becomes noticeable. Concomitantly, or shortly thereafter, parents report personality changes and behavioral issues. Typically, within 2–3 years after symptom onset, total vision loss occurs, and seizures begin. This is followed by declining speech, progressive loss of motor coordination, and cardiac involvement. Psychosis, hallucinations and/or dementia can appear anytime during the disease. Eventually, children become wheelchair-bound, then bedridden, and die in their late teens or early twenties.

### 2.1 Trial Description

This is an open label study in 6 subjects in 2 centers to assess the safety, pharmacokinetics (PK), and efficacy of the maximum tolerable dose (MTD) of oral miglustat (100 mg once daily [QD] to 200 mg 3 times daily [TID]) in subjects  $\geq$  17 years of age with CLN3 disease.

The study sites are Texas Children's Hospital (TCH) and National Institutes of Health Clinical Center (NIH CC).

- Screening visit, screening confirmation and the end-of-study visit for follow-up safety assessments will be conducted by the TCH. Eligibility will be confirmed by TCH after all inclusion/exclusion criteria are assessed; screening confirmation decision will be communicated to subjects via telephone call by TCH. TCH will also review all subject safety data throughout the duration of the study. TCH will also confirm remotely the final enrollment after NIH baseline (V2).
- Baseline, every 6 months visit and end-of-treatment visit for efficacy assessments will be conducted at NIH CC.
- Additional safety assessments will be performed at the Local Health Center /Subject's Home and at the NIH CC as per protocol.
- Patients will have their last efficacy visit at National Institutes of Health (NIH) at week 78 and their last on-treatment visit at Texas Children's Hospital (TCH), and will continue to be treated until they can be switched to an early access program.

The study includes a dose-titration period of 9 weeks. Subjects will be assigned to miglustat at Week 1 and dosing will be escalated weekly as presented in Table 1-1 of the protocol.

Treatment with miglustat will begin at a dose of 100 mg QD. If the initial dose of miglustat is well tolerated, then the dose will be increased weekly until the MTD for a subject is reached. The dose increment is 100 mg. If needed for tolerability reasons, a dose may be repeated for 1 or more weeks prior to increasing. If a dose is not tolerated (based on the occurrence of treatment-emergent adverse events (TEAEs) and at the discretion of the TCH Principal Investigator (PI)), the dose may be adjusted downward to the previous dose. Dose increases may resume if there is time left in the titration scheme and at the discretion of the TCH PI; otherwise, this lower dose

becomes the subject's MTD. If a subject has not reached the maximum dose (600 mg/d) by Week 8, the Week 8 dose will be subject's MTD.

Once the dose titration and PK sampling period are completed, subjects will continue their MTDs during the maintenance period. Temporary or permanent dose reductions of miglustat for tolerability are permitted at any time during the maintenance period of the study.

An early access program is planned for subjects who wish to continue the treatment. This early access program will be described in a separate protocol.

## **2.2 Study Sample Size Determination**

A total of six subjects will be enrolled in the study. Due to the ultra-rare nature of CLN3 disease, sample size is based on subject availability and not a statistical determination.

## **2.3 Treatment Assignment and Binding**

This is an open-label study. All subjects will receive miglustat.

## **2.4 Schedule of Assessments and Procedures**

See section 1.3 Schedules of Activities of the protocol for a tabular representation of the schedule of assessments.

### 3 OBJECTIVES AND ENDPOINTS

The study objectives and endpoints are presented in [Table 1](#) below.

**Table 1. Study Objectives and Endpoints**

Objectives	Endpoints
Primary	

 
To assess the safety and tolerability of the Batten-1 treatment regimen over the study period
 
	
 
Incidence of treatment-emergent adverse events (TEAEs) and serious adverse events (SAEs);
 
Changes from baseline in clinical laboratory tests (hematology, chemistry, and urinalysis), 12-lead electrocardiogram (ECG) findings, slit lamp evaluation, vital signs (heart rate and blood pressure) as well as physical and neurological examinations
 

Secondary	

 
To assess the pharmacokinetics (PK) of miglustat in subjects with CLN3 disease
 
	
 
Week 1 first dosing: Maximum plasma concentration (Cmax), Time to Cmax (Tmax), area under the concentration-time curve calculated to the last observable concentration at time t (AUC 0-t), area under the concentration-time curve extrapolated to infinity (AUC 0-∞), elimination half-life (T1/2)
 
Week 9 - Repeated dose (steady state): Cmin, Cmax, Tmax, AUC 0-8hr
 

 
To assess the effect of the Batten-1 treatment regimen on the longitudinal progression of clinical symptoms of CLN3 disease
 
	
 
Unified Batten Disease Rating Scale (UBDRS)
 
Seizure frequency (diaries)
 
Vineland Adaptive Behavior Scales, Version 3 (Communication, Daily Living Skills, Socialization, and Motor Skills domains)
 
Ophthalmic assessments including visual acuity, visual fields (if feasible), and optical coherence tomography (OCT)
 
Magnetic resonance imaging (MRI)
 

Exploratory	

 
To assess potential biomarkers of CLN3
 
	
 
Measure biomarkers in cerebrospinal fluid (CSF), blood and urine and CSF concentration of miglustat
 

#### 4 ANALYSIS POPULATIONS

The **Safety Population** will consist of all subjects who enroll in the study and receive at least 1 dose of study medication.

The **PK Population** will consist of subjects who received at least 1 dose of study drug and had a full PK sample set drawn per protocol for that day.

PK Population is used for all PK analyses. PK analyses are performed by [REDACTED] PK group, described in PK Analysis Plan, and reported in PK Analysis Report. PK analyses are not in scope of this SAP.

The **Efficacy Population** will consist of the subjects who received at least 1 dose of study medication and had at least 1 follow-up efficacy assessment, defined as at least one post-baseline Unified Batten Disease Rating Scale assessment.

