### **8.3 Analysis Populations**

The Safety Population will consist of all subjects who enroll in the study and receive at least 1 dose of study medication.

The PK Population will consist of subjects who received at least 1 dose of study drug and had a full PK sample set drawn per protocol for that day.

The Efficacy Population will consist of the subjects who received at least 1 dose of study medication and had at least 1 follow-up efficacy assessment.

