## **5.2 Secondary Endpoints**

All efficacy summaries described below will be analyzed using the Efficacy Population; listings will use All Screened Subjects.

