### **5.2.2 Seizure Frequency**

Seizure frequency will be collected in subject diaries and all seizures reported in the diaries will also be reported as AEs on the adverse events eCRF page.

For the purpose of summarizing seizures, the more granulated information from AE pages will be used. Each AE with preferred term including the word "seizure" will be considered a seizure for the purpose of this analysis.

For each subject the number of seizures per the following 3-month intervals will be calculated:

1. Pre-treatment,
2. Baseline to month 3 (study days 1 to 90; both inclusive),
3. 4 to 6 months (study days 91 to 180; both inclusive),
4. 7 to 9 months (study days 181 to 270; both inclusive),
5. 10 to 12 months (study days 271 to 360; both inclusive),
6. 13 to 15 months (study days 361 to 450; both inclusive),
7. 16 to 18 months (study days 451 to 540; both inclusive),
8. After 18 months (study day 541 and onwards),
9. Entire study duration (all previous combined).

Qualifying AE start days will be compared with the study days above to determine in which time interval the seizure occurred. For study day 1, treatment start time and AE start time will additionally be compared. In case of missing or partial AE start dates, imputation rules provided in section [8.1](#) will be used for determining the interval in which the seizure occurred.

Summary statistics of seizure counts for all subjects in the Efficacy Population will be provided by time interval. Individual seizure counts by time interval will be provided in a listing.

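### An undeclared SAP change makes a post-baseline UBDRS the entry ticket to the seizure-count summary, so a treated subject without one is dropped despite having seizure data

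*SAP*

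**What the plan says.** Protocol 8.3 defines the Efficacy Population as subjects who "received at least 1 dose of study medication and had at least 1 follow-up efficacy assessment". It does not say which assessment. Protocol 7.3 names seizure frequency by diary among the efficacy assessments, and Tables 1-3 to 1-5 place the diary under that heading.

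SAP 4 repeats the definition and then fixes its meaning: the follow-up assessment is "defined as at least one post-baseline Unified Batten Disease Rating Scale assessment". SAP 1.1, which sets out changes from the protocol, has two entries (an extra MedDRA level in the adverse event tables, and newer coding dictionaries). The population is not among them.

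SAP 5.2 gives the scope: "All efficacy summaries described below will be analyzed using the Efficacy Population; listings will use All Screened Subjects". SAP 5.2.2 repeats it for seizures: "Summary statistics of seizure counts for all subjects in the Efficacy Population will be provided by time interval". On the source of the counts it says: "For the purpose of summarizing seizures, the more granulated information from AE pages will be used".

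**The concern.** Under the protocol wording, a dosed subject with one diary collected after the first dose has a follow-up efficacy assessment and belongs in the population. Under the SAP wording the same subject does not belong until a UBDRS is done. Whether a subject enters the table for one endpoint is thus decided by whether a different endpoint was measured, and that second measurement is first scheduled about six months into treatment.

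The seizure summary is then conditional on staying long enough, or cooperating enough at termination, to be rated. Subjects who stop early for tolerability or worsening disease are the ones most likely to lack a rating. In an open-label study of six, one such subject can visibly alter a mean, median or range. SAP 5.2.2 is also the only planned summary of this secondary endpoint over time.

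**Working it through.** There is no sample-size or power figure to reproduce. Protocol 8.10 and SAP 2.2 base the six subjects on availability. The check compares the definitions with the schedule.

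**Inputs**
- Day convention: Table 1-3 sets Week 1 = Day 1 and Week 9 = Day 57, so Week w = Day 7(w − 1) + 1.
- UBDRS: Table 1-2 shows baseline, then Weeks 26, 52 and 78, each ± 1 month.
- Diary: daily from screening. Collections before Week 26 are at Weeks 5 and 9 (Table 1-3) and Weeks 10, 14 and 22 (Table 1-4).
- Seizure intervals: Days 1-90, 91-180, 181-270 and so on (SAP 5.2.2).
- Subjects: 6 (SAP 2.2).

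**When the first UBDRS falls.** Week 26 = 7 × 25 + 1 = Day 176. Taking a month as 30 days, the window is Days 176 − 30 = 146 to 176 + 30 = 206.

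**When seizure data exist.** Diary collections fall on Days 29, 57, 64, 92 and 148. A subject meets the protocol definition from the first of these, about 147 days before the nominal UBDRS (176 − 29 = 147).

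**Worked case: the subject leaves on Day 175 with no UBDRS.**
- Interval 1: 90 of 90 days observed.
- Interval 2: 175 − 90 = 85 of 90 days (94.4%).
- Interval 3 onwards: 0 days.
- Protocol definition: included, N = 6. SAP definition: excluded, N = 5. Share lost: 1/6 = 16.7%. Two such subjects would be 2/6 = 33.3%.

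**How likely is at least one?** The documents give no dropout rate. If p is the assumed chance that a subject leaves without any post-baseline UBDRS, the chance of at least one among six is 1 − (1 − p)^6:

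| Assumed p | Chance of at least one |
|---|---|
| 5% | 26.5% |
| 10% | 46.9% |
| 20% | 73.8% |

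These figures show the range before any outcome is known. SAP 6 says all six completed titration, so the only losses still possible are between then and the first UBDRS.

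**Would a UBDRS be done at discontinuation?** The protocol gives two answers.
- Section 5.4.1 calls for an early termination visit at NIH for efficacy. If that is not possible, it allows a remote visit or, at the least, a phone contact for adverse events. Section 5.4.2 adds that missing these procedures is not a deviation provided safety was preserved.
- The early termination visit in Table 1-2 and the premature-discontinuation column of Table 1-5 show no UBDRS. Table 1-5 does schedule diary collection there.

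If the tables are followed, an early leaver yields seizure data but not the assessment that decides membership. These sections must be reconciled.

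**Other endpoints.** Table 1-2 puts ophthalmic exams at the same visits as the UBDRS. The Day 175 leaver therefore has no scheduled post-baseline ophthalmic exam, and those post-baseline summaries are the same under either definition.

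**The case against.** The strongest reply is that little is lost. SAP 5.2.2 says diary seizures are also entered as adverse events, so they appear in the Safety Population tables with event and subject counts. Individual counts by interval are listed, and listings cover all screened subjects. With six subjects and only descriptive statistics, a reader could find the missing one. Protocol 8 also leaves analysis detail to the SAP, and nobody was lost during titration. All of this stands, and it limits the consequence. It does not replace the table: the adverse event summaries are organised by MedDRA term, not by three-month interval, and a listing is not a summary.

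A second reply is that adding an early leaver could mislead. SAP 5.2.2 summarises raw counts with no rule for partial or unobserved intervals, so a truncated count, or zeros after departure, could look like few seizures. That is correct, and the fix has to deal with it.

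Three stronger readings are tempting but not supported:
- A reader might infer that leaving before Week 26 by itself excludes a subject. It does not. A UBDRS at the termination visit, in person or remote, keeps the subject in. The condition is having no post-baseline UBDRS.
- A reader might infer that ophthalmic results are lost too. On the shared schedule only the baseline exam is.
- A reader might infer that an excluded subject could have two complete seizure intervals. Day 176 comes before Day 180, so that needs departure after Day 180 with the Week 26 visit late or missed.

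**Conclusion.** The point holds for the seizure-count summary. SAP 4 is narrower than protocol 8.3, the change is not declared in SAP 1.1, and it ties a continuously recorded endpoint to an unrelated visit. Each affected subject removes 16.7% of the subjects from that summary, with up to 175 days of follow-up if departure comes before nominal Week 26.

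This assumes that a collected diary counts as a follow-up efficacy assessment, which protocol 7.3 and the schedule tables support, and that no UBDRS is obtained at discontinuation, on which the protocol is inconsistent. The documents do not say whether any subject left before a post-baseline UBDRS. If none did, the tables are identical under both definitions and only the missing entry in SAP 1.1 remains. The change is still worth making, because the rule should not depend on who happened to stay.

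**What to change.** 1. Summarise seizure counts by interval in the Safety Population. Restoring the protocol 8.3 definition is the alternative. The UBDRS requirement can stay for the UBDRS tables themselves.
2. Include each subject only in intervals in which they were under observation. Show days observed, or express counts per unit of observed time, so that short follow-up is not read as few seizures.
3. Record in SAP 1.1 any UBDRS restriction that is kept, with its reason.
4. Reconcile protocol 5.4.1 with Tables 1-2 and 1-5 on whether a UBDRS is done at early termination.

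No new data are needed for items 1 to 3. The cost is a few sentences in the SAP, slightly more programming, and an n that varies by interval and must be shown in the table.

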## 5 STATISTICAL METHODS

### 5.1 Primary Endpoints

The primary endpoints pertain to subject safety and will be summarized for the Safety Population. Details on primary endpoints analyses are provided in sections below.

#### 5.1.1 Adverse Events

**Non-treatment emergent adverse events** (AEs) will be collected from the time the subject screened into the study (date of signature of informed consent) until first administration of study drug.

Thereafter, all AEs are **treatment-emergent adverse events** (TEAEs) and will be recorded until the end of study visit has been performed. In all outputs, AEs with start date(time) on or after the study drug start date(time) will be considered as TEAEs (i.e., TEAE designation will be programmatically derived based on dates; eCRF checkbox for TEAE will not be used). In case it is impossible to determine whether an AE is treatment-emergent or not (i.e., AE occurs on day 1 but time is unknown), the AE will be considered a TEAE.

Partial start dates of AEs will be imputed according to section [8.1](#) for the determination of non-treatment emergent and treatment-emergent designations.

AEs will be coded based on the Medical Dictionary for Regulatory Activities (MedDRA) latest version available before the database lock. National Cancer Institute's Common Terminology Criteria for Adverse Events (CTCAE) v5.0 will be used for the grading of AEs by the investigators.

For summary tables, AEs with relatedness "Definite", "Probable", and "Possible" will be considered as "Related", AEs with relatedness "Unrelated" and "Unlikely" will be considered "Not Related" and AEs with relatedness "Not Applicable" will be reported as such. AEs with missing relatedness assessment will be considered as "Related" for summary tables and will be footnoted in applicable tables; listings will present relatedness data as collected (i.e., missing).

AEs with missing seriousness assessment will be considered as "Serious" for summary tables; listings will present seriousness data as collected (i.e., missing). Should AEs with missing seriousness be present at time of reporting, these will be footnoted in applicable serious adverse event tables.

AEs with missing severity assessment will be considered as "Grade 3" for summary tables; listings will present severity data as collected (i.e., missing). Should AEs with missing severity be present at time of reporting, these will be footnoted in applicable adverse event tables.

An overall summary of AEs will be produced, including counts and percentages of subjects with any incidence of:

1. AEs (including non-treatment emergent AEs),
2. TEAEs,

3. Non-serious TEAEs,
4. Serious TEAEs (TESAEs),
5. Related TEAEs,
6. Related serious TEAEs,
7. TEAEs by maximum CTCAE grade,
8. CTCAE Grade 3 or above TEAEs,
9. CTCAE Grade 3 or above related TEAEs,
10. TESAEs leading to death,
11. TEAEs leading to treatment discontinuation,
12. TESAEs leading to treatment discontinuation,
13. Related TEAEs leading to treatment discontinuation
14. TEAEs leading to study discontinuation.

Summaries of AEs by MedDRA system organ class (SOC), high level group term (HLGT) and preferred term (PT) will be sorted by overall incidence of SOC, HLTG and PT and will include the following:

1. TEAEs,
2. TEAEs leading to treatment discontinuation,
3. TESAEs,
4. TEAEs by maximum CTCAE grade,
5. TEAEs by closest relatedness.

When calculating the incidence of AEs, each subject will be counted only once within a MedDRA category (e.g., overall, SOC, HLTG, or PT). When AEs are summarized within levels of another AE assessment (e.g., relatedness or CTCAE grade), subjects will be counted once at the worst level of the assessment within the MedDRA category (e.g., closest relatedness or highest CTCAE grade).

With the exception of summary tables by maximum CTCAE grade and closest relatedness, event counts will be included in all TEAE tables in addition to subject counts.

Adverse event duration (days) will be calculated as:

$$\text{Adverse Event End Date} - \text{Adverse Event Start Date} + 1$$

Adverse event duration will only be calculated for events with complete start and end dates available (i.e., imputed, partial and missing values will not be used for duration calculation); duration will only be included in listings.

AE data will be listed. Additionally, an SAE listing will be created.

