#### 7.1.1 Adverse Events

##### 7.1.1.1 Definitions

Adverse events and laboratory parameters will be graded using the National Cancer Institute (NCI) Common Terminology Criteria for Adverse Events (CTCAE) v5, sample of which is provided in Appendix 7 (US Department of Health and Human Services, 2017).

Per ICH, an AE is defined as any untoward medical occurrence in a subject or clinical investigation subject administered a pharmaceutical product and which does not necessarily have a causal relationship with this treatment. An AE can therefore be any unfavorable or unintended sign (including an abnormal laboratory finding), symptom, or disease temporally associated with the use of a medicinal (investigational) product, whether or not related to the medicinal (investigational) product. The AE may be any of the following:

- A new illness
- An exacerbation of a sign or symptom or the underlying condition or of a concomitant illness under treatment
- Unrelated to participation in the clinical study or an effect of the study medication or comparator drug
- A combination of one or more of the above factors

No causal relationship with the study medication is implied by the use of the term adverse event.

Planned or elective surgical or invasive procedures for pre-existing conditions that have not worsened are not AEs. However, any complication that occurs during a planned or elective surgery is an AE. Conditions leading to unplanned surgical procedures may be AEs.

When an AE occurs after written consent has been obtained but before the first dose of study drug, the AE will be considered a non-treatment emergent AE. An AE that occurs from the time the subject receives his/her first dose of study drug until his/her last study visit will be considered a treatment-emergent AE regardless of the assessed relationship to the administration of the study drug.

For the recording of pregnancy and relevant laboratory data see [Section 7.1.1.2](#).

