### **Severity of Adverse Event:**

Severity will be categorized using criteria based on CTCAE v.5:

Grade 1 Mild	asymptomatic or mild symptom; clinical or diagnostic observation only; intervention not indicated
Grade 2 Moderate	minimal, local or noninvasive intervention indicated; limiting age-appropriate instrumental ADL
Grade 3 Severe	Severe or medically significant but not immediately life-threatening; hospitalization or prolongation of hospitalization indicated, disabling; limiting self-care ADL
Grade 4 Life-threatening consequences	Urgent intervention indicated
Grade 5 death	Death related to AE

The term "severity" is used to describe the intensity of an event. This is not the same as "serious". Seriousness, not severity, serves as the guide for defining regulatory reporting obligations. The highest severity grade attained should be reported, for AEs with divergent severities.

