#### *7.1.1.2 Recording Adverse Events*

**Period: Subject Screening to the First Administration of Study Drug:** Non-treatment emergent AEs will be recorded from the time when the subject is screened into the study (date of signature of the informed consent) until first administration of study drug.

**Period: First Administration of Study Drug to Subject's Last Study Visit:** Thereafter all AEs are TEAEs (see Definitions, [Section 7.1.1.1](#)) and will be recorded until the end of study visit has been performed.

**Period After Last Study Visit:** Any SAE occurring after the subject's last study visit that the investigator becomes aware of but considered to be related to the study drug will be reported to the sponsor.

If an AE (serious or not) started during the study but did not end before the final follow-up visit, the investigator should make a reasonable effort to establish the outcome and the end date. If this is not possible, the outcome recorded at the final follow-up visit will be assumed to be the final outcome.

If an event stops and later restarts, all the occurrences must be reported. Adverse events assessed as related to study medication by the investigator and all SAEs must be followed up until resolution.

Signs/symptoms should be documented if a definite diagnosis cannot be established. The investigator should attempt to establish a diagnosis of the event based on signs, symptoms and/or other clinical information. In such cases, the diagnosis should be documented as the AE and/or SAE and not the individual signs/symptoms. If a diagnosis is accompanied by unusual symptoms, the diagnosis itself and the symptoms have to be reported separately.

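### TEAE status is set by onset alone, so a pre-dose adverse event kept as one record that worsens on miglustat drops out of the TEAE summaries

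*SAP*

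**What the plan says.** SAP 5.1.1 applies one test to every output: "AEs with start date(time) on or after the study drug start date(time) will be considered as TEAEs". The status is derived from dates, and the "eCRF checkbox for TEAE will not be used". A default toward TEAE opens with "In case it is impossible to determine whether an AE is treatment-emergent or not"; the case it names is a Day 1 event with no recorded time. SAP 8.1 imputes missing or partial start dates.

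The protocol uses the same logic. Section 7.1.1.1 treats an AE between consent and first dose as non-treatment-emergent, and counts as treatment-emergent "An AE that occurs from the time the subject receives his/her first dose of study drug until his/her last study visit". Section 7.1.1.2 says of the period after first dose: "Thereafter all AEs are TEAEs". Neither document says what happens when a pre-dose AE worsens after dosing.

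Two protocol rules govern how such an event is entered. Under severity: "The highest severity grade attained should be reported, for AEs with divergent severities". Under recording: "If an event stops and later restarts, all the occurrences must be reported". Against these, the AE definition in 7.1.1.1 lists an exacerbation among the things an AE may be.

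**The concern.** The primary endpoint is the incidence of TEAEs and SAEs. Apart from the first row, every line of the overall AE summary and every SOC/HLGT/PT table is restricted to TEAEs. If on-drug worsening stays in a record whose start date precedes first dose, the tables treat it as a pre-treatment event, whatever its final grade, seriousness, attributed relationship or consequence.

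This runs against the rest of SAP 5.1.1. There, undeterminable timing counts as TEAE, missing relatedness as related, missing seriousness as serious and missing severity as Grade 3. The result also depends on data entry: the same clinical course counts or does not count according to whether the site opened one record or two.

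Worsening is a relevant safety signal for this drug. Protocol 2.3.1.1 reports new or exacerbated tremor in about 30% of people with Gaucher disease on miglustat. The neurological examination in SAP 5.1.7 is summarised only as normal or abnormal, so deterioration within abnormal would not show there.

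**Working it through.** **1. Can the record exist?** AEs are collected from consent (Protocol 7.1.1.2). The pre-dose window is:
- about 4 weeks in the synopsis;
- Days -42 to -1 in Table 1-2, i.e. 42/7 = 6 weeks;
- under the travel exception (Table 1-2, footnote B), up to 3 months between the two inclusion visits plus 1 month to first dose, about 4 months.

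**2. What does the rule do with it?** Take an illustrative event, Grade 1 before first dose and Grade 3 on drug.
- One record, pre-dose start, highest grade reported: start < first dose, so 0 TEAEs and 0 subjects with a Grade 3 or above TEAE.
- Two records, the second starting at the worsening: 1 TEAE and 1 subject with a Grade 3 or above TEAE.

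The Day 1 default and the SAP 8.1 imputation do not reach a record with a complete pre-dose start date.

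**3. Overall-summary rows from which one such record is left out** (numbering as in SAP 5.1.1; row 1, all AEs, always keeps it):

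| Character of the record | Rows lost | Count of 14 |
|---|---|---|
| Non-serious, not related, Grade 1–2, no discontinuation | 2, 3, 7 | 3 |
| Same, but related | 2, 3, 5, 7 | 4 |
| Non-serious, related, Grade 3+ | 2, 3, 5, 7, 8, 9 | 6 |
| Serious, related, Grade 3+, no discontinuation | 2, 4–9 | 7 |
| Plus treatment discontinuation | adds 11, 12, 13 | 10 |
| Plus study discontinuation | adds 14 | 11 |
| Plus death | adds 10 | 12 |

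The ceiling is 14 − 1 (row 1) − 1 (row 3, which excludes row 4) = 12.

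**4. SOC/HLGT/PT tables.** The record is always missing from three of five: all TEAEs, by maximum grade, and by closest relatedness. Being serious adds one, and leading to treatment discontinuation adds one, for a maximum of 5.

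**5. Event counts.** Outside the by-grade and by-relatedness tables, "event counts will be included in all TEAE tables in addition to subject counts". That leaves 5 − 2 = 3 SOC/HLGT/PT tables with event counts. Each such record lowers the event count by 1 in one to three of them.

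**6. Subject incidence.** With N = 6 (SAP 2.2), one subject is 1/6 = 16.7 percentage points. The change is 16.7 if the subject has no other qualifying event in that row and 0 otherwise. In the by-grade and by-relatedness displays, a subject with other TEAEs in the category shifts level only if this record was the worst.

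**7. How likely is at least one affected subject?** The documents give no rate. If a share p of subjects had such a record (assumption), the chance of at least one among six is 1 − (1 − p)^6: 26.5% at p = 5%, 46.9% at 10%, 73.8% at 20% and 88.2% at 30%.

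**The case against.** The strongest reply is that the protocol already provides a route. An exacerbation may be an AE in its own right, and any AE occurring after first dose is a TEAE. A site that enters the worsening as a new record gets the right count. The severity rule says which grade to report and does not mention start dates. The eCRF completion guidelines, which might settle the matter, are not among these documents. The causality categories in 7.1.1.1 look for a reasonable or plausible time relation to dosing, so an investigator who attributes the worsening to miglustat has some reason to open a new record. That makes the larger row counts the less likely ones.

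The exposed set is also narrow:
- Pre-dose abnormal examination findings go to medical history, and adverse change from the baseline examination goes on the AE page (Protocol 7.1.6).
- Laboratory AEs are judged against pre-treatment values (Protocol 7.1.1.5).
- Laboratory, ECG, vital-sign and weight changes from baseline are summarised (SAP 5.1.2, 5.1.3, 5.1.5).
- Seizures are counted by start day with a pre-treatment interval (SAP 5.2.2).
- Over up to 116 weeks of treatment most subjects will probably have some TEAE, so the any-TEAE row is unlikely to move.

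All of this limits the size of the problem and does not remove it. Neither document requires worsening of a continuing event to be a new record; separate occurrences are required only after a stop and restart. Visible changes would fall mainly at preferred-term level or in sparse rows such as serious or Grade 3 and above.

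A further objection is that the definition would change after an open-label interim analysis on all six subjects (SAP 6). The change can only raise TEAE counts or leave them alone, so it cannot flatter the drug.

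**Conclusion.** The concern holds. The SAP implements the protocol's definition faithfully, so this is a gap common to both documents and not a SAP departure. Under it, a pre-dose AE kept as one record that worsens on miglustat is absent from 3 to 12 of 14 overall rows and from 3 to 5 of 5 SOC/HLGT/PT tables, with a subject-level effect of 0 or 16.7 points per row. The error is confined to summary counts: every AE and SAE is still listed, and no data are lost. It mainly concerns symptom-type events that begin before first dose.

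The conclusion assumes that at least one such event was entered as a single record. That is plausible from the recording rules but cannot be confirmed without the completion guidelines, and the number may be zero. The change should be made before lock; confidence is medium.

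**What to change.** Add to SAP 5.1.1, and log in SAP 1.1 as a change from the protocol definition:

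- An AE that starts before first dose and increases in CTCAE grade, or becomes serious, on or after first dose is a TEAE, counted once. If the worsening was entered as its own AE, only that record counts as the TEAE.
- Before database lock, query each AE ongoing at first dose for its grade at that time and the date of any worsening. The recorded action taken and, for SAEs, the dates on the SAE form can support the answer.
- If worsening is confirmed or cannot be excluded but its timing cannot be determined, count the AE as a TEAE at its recorded grade, with a footnote. This matches the section's other conservative defaults.
- List records where the derived status and the eCRF checkbox disagree, as a check only, because the documents do not say how the checkbox is completed.

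The cost is a short clause, one SAP 1.1 entry, one listing and a few retrospective queries in six subjects, with no new site assessment. On the downside, TEAE incidence may be slightly higher, the default may count an event that did not in fact worsen on drug, and grade at first dose may be hard to recover for old records.
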